4.2.2 SECONDARY ENDPOINTS

This study is not powered to detect statistically significant differences in cognitive or motor domains between

the Baseline and End of Study values. Secondary endpoints will be summarized over the study period from Baseline values using descriptive statistics.

Secondary Efficacy Endpoints:

- Change from baseline in the MoCA (Nasreddine 2005)(Appendix 1).
- Change from baseline in Continuity and Power of Attention, Working Memory, and Episodic Memory on the CDR-CCB (Wesnes 1977, Wesnes 2000).
- Change from baseline in D-KEFS Verbal Fluency (Delis 2001, Delis 2004, Emre 2004).
- Change from baseline in the MDS-UPDRS 1, 2, 3, and total score (Fahn 1987, Movement Disorders Task Force 2003)(Appendix 2).
- Change from baseline in the SE-ADL Scale (Schwab 1968)(Appendix 3).
- Change from baseline in the CISI-PD (Martinez-Martin 2006)(Appendix 4).
- Change from baseline in the PDQ-39 (Peto 1998)(Appendix 5).
- Change from baseline in the GDS-15 (Yesavage 1983)(Appendix 6).
- Change from baseline in the dCDT (Müller 2017).

Secondary Safety Endpoints:

- Change from baseline in clinical laboratory parameters.
- Change from baseline in vital sign measurements.
- Change from baseline in body weight.
- Change from baseline in the S-STs (Sheehan 2014)(Appendix 7).

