10.2 STATISTICAL HYPOTHESES

Because the primary objective of the study is safety and tolerability, the study is not designed to detect statistically significant differences between active and placebo on efficacy endpoints. The statistical approach toward secondary efficacy endpoints will be primarily descriptive; within-subject changes from baseline for each dosing group and among-group differences will be evaluated.

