10.4.3 ANALYSIS OF THE SECONDARY EFFICACY ENDPOINTS

The study is not powered to detect significant changes in cognition, motor function, activities of daily living, etc.; however, using available data from analysis of the secondary efficacy endpoints, including changes in scores from baseline, descriptive summaries will be developed. Of particular interest will be the within-subject changes from baseline and their distribution around a null value of zero and a comparison between groups to evaluate any trends in differences between subjects randomized to active and placebo agents. Appropriate paired sample tests (paired t-test or Wilcoxon Signed Rank tests) may be conducted to evaluate within-subject changes from baseline, using a two-tailed α -level of 0.05. Between-group differences may be assessed by One-way ANCOVA or its nonparametric equivalent test.

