2.2.2.2. Secondary Efficacy Endpoint(s)

The secondary efficacy endpoints of this study include the following:

- Change from baseline in the Montreal Cognitive Assessment (MoCA).
- Change from baseline in Continuity and Power of Attention, Working Memory, and Episodic Memory on the Cognitive Drug Research Computerized Cognition Battery (CDR-CCB).
- Change from baseline in Delis-Kaplan Executive Function System (D-KEFS) Verbal Fluency.
- Change from baseline in the Movement Disorder Society's Unified Parkinson's Disease Rating Scale (MDS-UPDRS) 1, 2, 3, and total score.
- Change from baseline in the Schwab and England Activities of Daily Living (SE-ADL) Scale.
- Change from baseline in the Clinical Impression of Severity Index – PD (CISI-PD).
- Change from baseline in the PD Quality of Life Questionnaire-39 (PDQ-39).
- Change from baseline in the Geriatric Depression Scale-15 (GDS-15).
- Change from baseline in the digital clock drawing test (dCDT).

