8.2.5. Schwab and England Activities of Daily Living Scale (SE-ADL)

The SE-ADL evaluates patients' perceptions of global functional capacity and dependence. Scoring is expressed in terms of percentage, in 10 steps from 100 to 0 (100%, normal status; 0%, bedridden with vegetative dysfunction), so that the lower the score, the worse the functional status. The scoring is as follows:

Scale for the SE-ADL Rating	Description
100%	Completely independent. Able to do all chores without slowness, difficulty, or impairment. Essentially normal. Unaware of any difficulty.
90%	Completely independent. Able to do all chores with some degree of slowness, difficulty and impairment. May take twice as long. Beginning to be aware of difficulty.
80%	Completely independent in most chores. Takes twice as long. Conscious of difficulty and slowing.
70%	Not completed independent. More difficulty with some chores. X3-4 as long in some. May spend a large part of the day with chores.
60%	Some dependency. Can do most chores, but exceedingly slowly and with much effort. Errors; some impossible.
50%	More dependent. Help with ½ of chores. Difficulty with everything.
40%	Very dependent. Can assist with all chores but few alone.
30%	With effort, now and then does a few chores alone or begins alone. Much help needed.
20%	Nothing alone. Can do some slight help with some chores. Severe invalid.
10%	Totally dependent, helpless. Complete invalid
0%	Vegetative functions such as swallowing, bladder and bowel functions are not functioning. Bedridden.

The SE-ADL is measured at Baseline (Visit 2), Week 8 (Visit 10), and Week 24 (Visit 19). The number and percentage of subjects falling in each category at each time point will be displayed by treatment group. A 2-sided Cochran-Mantel-Haenszel (CMH) test will be performed at the 5% significance level to determine whether there is a significant relationship between treatment group and level of independence.

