8.2.6. Clinical Impression of Severity Index – Parkinson’s Disease (CISI-PD)

The CISI-PD is a severity index formed by four items (motor signs, disability, motor complications, and cognitive status), rated 0 (not at all) to 6 (very severe or completely disabled). CISI-PD is measured at Baseline (Visit 2), Week 8 (Visit 10), and Week 24 (Visit 19). Change from baseline to study visit in each item will be summarized by treatment group. A test of hypothesis comparing mean scores between baseline and subsequent study visits will be conducted using a 2-sided paired t-test or Wilcoxon signed rank test, as appropriate. The null hypothesis is that the mean change from baseline to subsequent visit is 0.

Mean change from baseline in Total score will be compared between treatment groups using an ANCOVA model with treatment, visit, and treatment by visit interaction as a main effects and baseline score, age, and ApoE genotype as covariates.

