Table 14.2.3.6	Complete	Mean Change from Baseline in MDS-UPDRS Parts 1, 2, and 3 and Parts 1-3 Total Score by Study Visit and Treatment, Tabulation of Fitted Summary Statistics from ANCOVA	
Table 14.2.4.1	Evaluable	Summary of SE-ADL by Study Visit and Treatment	
Table 14.2.4.2	Per Protocol	Summary of SE-ADL by Study Visit and Treatment	
Table 14.2.4.3	Complete	Summary of SE-ADL by Study Visit and Treatment	
Table 14.2.5.1	Evaluable	Summary of Change from Baseline in CISI-PD Scores by Treatment	
Table 14.2.5.2	Evaluable	Mean Change from Baseline in CISI-PD Total Score by Study Visit and Treatment, Tabulation of Fitted Summary Statistics from ANCOVA	
Table 14.2.5.3	Per Protocol	Summary of Change from Baseline in CISI-PD Scores by Treatment	
Table 14.2.5.4	Per Protocol	Mean Change from Baseline in CISI-PD Total Score by Study Visit and Treatment, Tabulation of Fitted Summary Statistics from ANCOVA	

Number	Set	Title	Include in Interim Efficacy Analysis?
Table 14.2.5.5	Complete	Summary of Change from Baseline in CISI-PD Scores by Treatment	
Table 14.2.5.6	Complete	Mean Change from Baseline in CISI-PD Total Score by Study Visit and Treatment, Tabulation of Fitted Summary Statistics from ANCOVA	
Table 14.2.6.1	Evaluable	Summary of Change from Baseline in PDQ-39 Scores by Treatment	
Table 14.2.6.2	Evaluable	Mean Change from Baseline in PDQ-39 Total Score by Study Visit and Treatment, Tabulation of Fitted Summary Statistics from ANCOVA	
Table 14.2.6.3	Per Protocol	Summary of Change from Baseline in PDQ-39 Scores by Treatment	
Table 14.2.6.4	Per Protocol	Mean Change from Baseline in PDQ-39 Total Score by Study Visit and Treatment, Tabulation of Fitted Summary Statistics from ANCOVA	
Table 14.2.6.5	Complete	Summary of Change from Baseline in PDQ-39 Scores by Treatment	
Table 14.2.6.6	Complete	Mean Change from Baseline in PDQ-39 Total Score by Study Visit and Treatment, Tabulation of Fitted Summary Statistics from ANCOVA	
Table 14.2.7.1	Evaluable	Summary of GDS-15 Categories by Study Visit and Treatment	
Table 14.2.7.2	Evaluable	Summary of Change from Baseline in GDS-15 Score by Treatment	
Table 14.2.7.3	Evaluable	Mean Change from Baseline in GDS-15 Total Score by Study Visit and Treatment, Tabulation of Fitted Summary Statistics from ANCOVA	
Table 14.2.7.4	Per Protocol	Summary of GDS-15 Categories by Study Visit and Treatment	
Table 14.2.7.5	Per Protocol	Summary of Change from Baseline in GDS-15 Score by Treatment	

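### SE-ADL is defined as change from baseline, but its SAP section and tables plan only category counts per visit and a CMH test on level

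*SAP*

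**What the plan says.** Protocol 4.2.2 lists the endpoint as "Change from baseline in the SE-ADL Scale", and SAP 2.2.2.2 repeats it: "Change from baseline in the Schwab and England Activities of Daily Living (SE-ADL) Scale". Protocol 10.2 adds that "within-subject changes from baseline for each dosing group and among-group differences will be evaluated". Protocol 10.4.1 says the secondary endpoints will be summarised over time so that within-subject change can be assessed. Protocol 10.4.3 gives the emphasis: "Of particular interest will be the within-subject changes from baseline and their distribution around a null value of zero".

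SAP 8.2.5 describes a scale scored from 100% to 0% in 10-point steps, measured at Visits 2, 10 and 19. Its descriptive plan is: "The number and percentage of subjects falling in each category at each time point will be displayed by treatment group". Its only inference is: "A 2-sided Cochran-Mantel-Haenszel (CMH) test will be performed at the 5% significance level", relating treatment group to level of independence. The CMH statistic is not named and no strata are given.

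The table list in SAP 13.2 has one SE-ADL title per analysis set: "Summary of SE-ADL by Study Visit and Treatment". The shell shows counts for each level with a CMH p value at every visit, baseline included. Its footnote takes the baseline value from Visit 1.

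**The concern.** Someone following SAP 8.2.5, the table list and the shell exactly would never report SE-ADL change. The result would describe level at each visit and compare the arms on level. That is a different quantity from the defined endpoint, and the substitution is not recorded in SAP Section 10 (Changes from Planned Analysis).

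Two things are at stake. First, the spread of individual change is missing. The trial hopes efficacy trends will help size later studies (Protocol 10.5, SAP 3.2), so that figure is useful. Second, the between-arm comparison as written makes no stated use of baseline. If baseline predicts follow-up, precision is lost and a chance baseline difference between arms goes uncorrected.

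**Working it through.** **1. SE-ADL beside a scale on the same schedule.** SAP 8.2.6 says "CISI-PD is measured at Baseline (Visit 2), Week 8 (Visit 10), and Week 24 (Visit 19"), the same three visits as SE-ADL.

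| | SE-ADL | CISI-PD |
|---|---|---|
| Defined endpoint | change | change |
| Descriptive summary | counts per level per visit | change by arm |
| Within-subject test | none | paired t or signed rank |
| Between-arm comparison | CMH on level, strata not stated | ANCOVA on change with baseline, age and ApoE |
| Tables per analysis set | one | two |

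In the table list, MoCA, D-KEFS, MDS-UPDRS, CISI-PD, PDQ-39, GDS-15 and dCDT each have a change summary and an ANCOVA table. SE-ADL is the only one of these eight scales with neither. (CDR-CCB has its own plan.)

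**2. Generic rules.** SAP 6.1.7 derives change as current value minus baseline. SAP 8.2 gives a signed-rank rule for non-normal data. SAP 6.1.2 puts baseline scores into efficacy models. None of these is taken up in 8.2.5, the table list or the shell. Listing 16.2.6.4 carries only each subject's level.

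**3. What the counts can recover.** An arm's mean at a visit is Σ(level × count) / Σ(count). The difference between visit means is the mean change, exact if the same subjects attend and approximate with dropout. The spread of change cannot be recovered. Take two subjects at 70% and 80% at both visits by count. Either nobody moved (changes 0 and 0, SD 0) or they swapped (changes +10 and −10, SD √200 = 14.1). The table is identical in both cases.

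**4. Size of the precision loss.** The plan's own sample figure reproduces: 90 × (1 − 0.25) = 67.5, stated as about 68. At 2:1 that is 68 × 2/3 = 45.3 and 68/3 = 22.7, so 45 v 23. The documents give no SE-ADL mean, SD, correlation or effect, so everything below is assumed.

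*Closed form*, 80% power, two-sided 5%: detectable difference = (1.96 + 0.842) × s × √(1/22.67 + 1/45.33) = 2.802 × 0.257 × s = 0.72 s. For level, s = 1 SD. With baseline adjustment s = √(1 − ρ²), which gives 0.62, 0.52 and 0.43 SD at ρ = 0.5, 0.7 and 0.8.

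*Simulation*, 10,000 trials per cell: mean 75, SD 12, scores rounded to 10-point steps, true difference 6 points, 45 v 23, one visit, baseline the only covariate. Power:

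| Baseline correlation | Row-mean CMH on level | Rank ANCOVA | Row-mean CMH stratified by baseline category |
|---|---|---|---|
| 0.3 | 46–47% | 46% | 46% |
| 0.5 | 46–47% | 53% | 52% |
| 0.7 | 46–47% | 67% | 66% |
| 0.8 | 46–47% | 78% | 77% |

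The general-association form of CMH has 21% power, so leaving the statistic unnamed also matters. Type I error is 4.7–5.1% for row-mean CMH, 3.1–3.6% for general association and 4.9–5.4% for rank ANCOVA.

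*Sensitivity*, row-mean CMH v rank ANCOVA at correlations 0.3/0.5/0.7/0.8:
- 36 v 18 (20% fewer): 38–39% v 39/44/57/68%
- SD 9, 45 v 23: 68–69% v 69/75/87/93%
- SD 16, 45 v 23: 29–30% v 29/34/45/56%

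*Chance baseline difference.* At SD 12 and 45 v 23, a difference of 3 points or more arises in 33% of null trials. Row-mean CMH error is 5.7/8.6/12.1/12.9% in those and 4.4/3.3/1.6/0.9% in the rest. At 0.7 this nets to 0.33 × 12.1 + 0.67 × 1.6 = 5.1%. Rank ANCOVA and the baseline-stratified CMH stay within 4.4–5.4% in both groups.

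**The case against.** The case for leaving the plan alone has substance. The trial is stated repeatedly to be unpowered for efficacy. Protocol 10.4.1 allows categorical analysis, and Protocol 10.4.3 makes paired tests and between-group ANCOVA optional. The scale is ordinal, and the generic rules in SAP 6.1.2, 6.1.7 and 8.2 mention baseline, change and a signed-rank test. It follows that choosing a CMH test is not itself a breach. It does not follow that change can go unsummarised: Protocol 10.2 and 10.4.1 commit to that, and the generic rules never reach an SE-ADL output.

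Several stronger readings are tempting and are not supported:

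- **That nothing about change can be estimated.** Arm-level mean change can be approximated from the counts (step 3). What is lost is the within-subject information.
- **That the CMH test ignores baseline.** The SAP does not state the strata. Baseline stratification is unspecified, which is not proof that it is absent.
- **That the CMH test gives false positives.** Its error is high in imbalanced trials and low in the others, and about 5% overall.
- **That the Anderson-Darling rule will send SE-ADL to rank ANCOVA.** SAP 8.2 does not say which data are tested. At SD 12, simulated rejection of normality is 99.9–100% for change scores but 12–31% for ANCOVA residuals.
- **That a later trial's size is uncertain by a factor of 2.9.** With n per arm = 2 × (SD × 2.802 / 6)², SDs of unadjusted change of 14.55 and 8.51 give 93 and 32. With baseline adjustment, residual SDs of about 11.7 and 8.0 give 60 and 28, a factor of 2.1. Both ranges rest on assumed correlations of 0.3 to 0.8, and no document says SE-ADL would size a later study.

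**Conclusion.** The gap is real and limited. The endpoint is change from baseline, and the SE-ADL section and tables do not report the within-subject distribution, the SD of change, or any paired or baseline-adjusted result. The test that is planned is valid.

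The precision lost depends on a correlation the documents do not give: none at 0.3, and about 20 points of power (46% v 67%) at 0.7. Those figures use a simpler model than the one planned for CISI-PD, which adds visit, treatment-by-visit interaction, age and ApoE genotype, so they are illustrative. The change summary follows directly from the endpoint definition and Protocol 10.2. The adjusted comparison is better practice and consistent with the other scales, but the protocol does not require it.

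This should be corrected, but it touches one unpowered secondary endpoint. The primary safety analysis is unaffected.

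**What to change.** In SAP 8.2.5, the table list and the shells:

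1. For the Evaluable, Per Protocol and Complete Sets, add a summary of SE-ADL change from Visit 2 to Visits 10 and 19 by arm (n, mean, SD, median, range), or a baseline-to-visit shift table, with the paired t-test or signed-rank test. Report it whatever the normality result, because rank ANCOVA gives no difference in SE-ADL points.
2. Make the between-arm comparison baseline-adjusted. Use either ANCOVA or rank ANCOVA as for CISI-PD, or a CMH test specified as row-mean-score and stratified by baseline SE-ADL category.
3. Keep the category table as description.
4. Correct the Table 14.2.4.1 footnote from Visit 1 to Visit 2, the first visit at which SE-ADL is measured.

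The cost is SAP wording and a few tables: about six with ANCOVA (two for each of three sets), or three if the stratified CMH p value stays in the existing table. No new data are needed.

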8.2.6. Clinical Impression of Severity Index – Parkinson’s Disease (CISI-PD)

The CISI-PD is a severity index formed by four items (motor signs, disability, motor complications, and cognitive status), rated 0 (not at all) to 6 (very severe or completely disabled). CISI-PD is measured at Baseline (Visit 2), Week 8 (Visit 10), and Week 24 (Visit 19). Change from baseline to study visit in each item will be summarized by treatment group. A test of hypothesis comparing mean scores between baseline and subsequent study visits will be conducted using a 2-sided paired t-test or Wilcoxon signed rank test, as appropriate. The null hypothesis is that the mean change from baseline to subsequent visit is 0.

Mean change from baseline in Total score will be compared between treatment groups using an ANCOVA model with treatment, visit, and treatment by visit interaction as a main effects and baseline score, age, and ApoE genotype as covariates.

8.2.7. Parkinson’s Disease Quality of Life Questionnaire-39 (PDQ-39)

The long form of the PDQ has 39 questions, with eight dimensions:

- Mobility (10 items)
- Activities of daily living (6 items)
- Emotional well-being (6 items)
- Stigma (4 items)
- Social support (3 items)
- Cognitions (4 items)
- Communication (3 items)
- Bodily discomfort (3 items)

The frequency of each event is recorded as one of five options, with each option assigned a numeric value as indicated: never (0), occasionally (1), sometimes (2), often (3), or always/cannot do at all (4). It is scored on a scale of 0-100 with lower scores indicating better health and high scores indicating more severe symptoms. Derivations for each of the subscores and total score are described in Section 6.1.7.

The PDQ-39 will be collected at Baseline (Visit 2), Week 4 (Visit 9), Week 8 (Visit 10), Week 20 (Visit 18), and Week 24 (Visit 19).

Change from baseline to study visit in the PDQ-39 Mobility, Activities of Daily Living, Emotional Well-Being, Stigma, Social Support, Cognitions, Communication, and Bodily Discomfort subscores and PDQ-39 Total score will be summarized by treatment group. A test of hypothesis comparing mean scores between baseline and subsequent study visits will be conducted using a 2-sided paired t-test or Wilcoxon signed rank test, as appropriate. The null hypothesis is that the mean change from baseline to subsequent visit is 0.

Mean change from baseline in Total score will be compared between treatment groups using an ANCOVA model with treatment, visit, and treatment by visit interaction as a main effects and baseline score, age, and ApoE genotype as covariates.

8.2.8. Geriatric Depression Scale-15 (GDS-15)

The GDS-15 is a shortened form of a 30-item questionnaire in which participants are asked to respond by answering yes or no in reference to how they felt over the past week. Of the 15 items, 10 indicate the presence of depression when answered positively, while the rest (question numbers 1, 5, 7, 11, 13) indicate depression when answered negatively. Each item is recorded as yes or no which is assigned a numeric value of 1 or 0, respectively. The final score is the tally of the number of depressive answers with the following scores indicating depression:

- 0-4 No depression
- 5-10 Suggestive of a mild depression
- 11 + Suggestive of severe depression

Derivations for the final score is described in Section 6.1.7. The GDS-15 will be collected at Baseline (Visit 2), Week 8, (Visit 10) and Week 20 (Visit 18). The number and percentages of subject responses will be summarized by treatment group and visit. Change from baseline to study visit in GDS-15 total score will be summarized by treatment group.

8.2.9. Digital Clock Drawing Test (dCDT)

The pen-like dCDT device gathers the x-y coordinates that describe the movement of the stylus as it changes its position during the assessment. It also assesses when the stylus or writing device is not exerting pressure on the writing surface (i.e., in-air movements performed by the hand while transitioning from one stroke to the next).

The dCDT will be collected at Baseline (Visit 2), Week 1 (Visit 8), Week 8 (Visit 10), Week 13 (Visit 16), and Week 20 (Visit 18).

The dCDT score is a number from 0 and 100 that represents a person's overall cognitive function as assessed by DCTclock. The score will be classified as within normal limits, indeterminate, outside normal limits, or unanalyzable based on cut scores and test performance.

Change from baseline to study visit in dCDT score will be summarized by treatment group. A test of hypothesis comparing mean scores between baseline and subsequent study visits will be conducted using a 2-sided paired t-test or Wilcoxon signed rank test, as appropriate. The null hypothesis is that the mean change from baseline to subsequent visit is 0.

Mean change from baseline in dCDT score will be compared between treatment groups using an ANCOVA model with treatment, visit, and treatment by visit interaction as a main effects and baseline score, age, and ApoE genotype as covariates.

The number and percentage of subjects falling in each classification at each time point will be displayed by treatment group.

The cognitive features within the drawing efficiency, simple motor, information processing, and spatial reasoning composite scales will be listed.

8.3. Exploratory Efficacy Analysis

8.3.1. Apolipoprotein E (ApoE) Genotype Testing

DNA for ApoE analysis will be obtained from a blood serum sample collected at Visit 3 to determine ApoE genotype at baseline. ApoE genotype will be listed and summarized as part of demographics and baseline characteristics. See Section 7.3. The number and proportion of subjects with the genotype for each allele will be presented.

8.3.2. Magnetic Resonance Imaging (MRI)

MRI will be used to evaluate subjects' eligibility for inclusion in the study at screening. Structural images will be interpreted by a central reader at screening and any exclusionary findings will be reported. Where available, functional imaging will also be acquired to assess for functional connectivity as measured by tf-fMRI and cerebral blood flow as measured by ASL MRI. In consenting subjects, an additional MRI at Visit 16 will assess for changes in brain atrophy as measured by MRI, functional connectivity as measured by tf-fMRI, and cerebral blood flow as measured ASL MRI. During the MRI, the subject will be asked to lie on a narrow bed in a large tunnel while images are captured by the MRI machine. Participation in the screening MRI is required, while participation in the additional MRI at Visit 16 is optional and not required for inclusion in the study.

